9.1.2. Summary Measure

Descriptive statistics (n, arithmetic mean, standard deviation [SD], 95% CI, minimum, median and maximum) will be calculated for all PK concentrations over time and for the

CONFIDENTIAL

208564

derived PK parameters. In addition, for log-transformed PK parameter variables (i.e. Cmax, AUC(0-t), AUC(0-inf), CL/F, Vss/F, t1/2), geometric mean, 95% CI and %CV_b will be provided. Plots of mean concentrations will also include standard deviation [SD] for the mean.

9.1.3. Population of Interest

The primary pharmacokinetic analyses will be based on the “Pharmacokinetic” population, unless otherwise specified.

9.1.4. Strategy for Intercurrent (Post-Randomization) Events

A ‘While on-study’ strategy will be implemented for intercurrent events.

- Withdrawn participants may be replaced in the study. Replacement participants will be dosed with the planned treatment of the withdrawn participant.
- All available data from participants who were withdrawn from the study will be analysed and listed, and all available planned data will be included in summary tables and figures, unless otherwise specified.
- Non quantifiable data will be handled as per GUI_51487
- If anomalous concentration data is identified, the pharmacokineticist will:
 - excludes the PK concentration data deemed to be anomalous
 - documents the reason for exclusion in the ‘Code’ folder of the Phoenix Project
 - communicates exclusion to Statistics and Programming

Note: Any exclusion of anomalous PK concentration data is documented in the clinical study report (CSR). Anomalous PK data is excluded from PK summaries and is flagged by asterisk or appropriate footnote in the PK data listings.

10. PHARMACODYNAMIC AND / OR BIOMARKER ANALYSES

10.1. Exploratory Pharmacodynamic (and / or Biomarker) Analyses

10.1.1. Endpoint / Variables

Parameter	Parameter description
Free OSM	Free OSM concentration in serum
Total OSM	Total OSM concentration in serum
TPO	Thrombopoietin concentration in serum
EPO	Erythropoietin concentration in platelet-poor plasma

10.1.2. Summary Measure

Descriptive statistics (n, arithmetic mean, standard deviation [SD], 95% CI, minimum, median and maximum) will be calculated for free and total OSM concentrations over time. Descriptive statistics (n, geometric mean and standard deviation [SD] on log scale, CVb%) will be calculated for log transformed total OSM concentration and ratio to baseline. Plots of individual, mean concentrations with SD and median concentrations with range for total OSM will be produced.

Total OSM parameters will be calculated by standard non-compartmental analysis according to current working practices and using the currently supported version of WinNonlin. All calculations of non-compartmental parameters will be based on actual sampling times. Total OSM, Cmax, Tmax, AUC(0-t), AUC(0-inf), %AUCex, t1/2, CL/V, Vss/V, tlast might be calculated with non-compartmental analysis, from the serum concentration-time data, as data permits.

Only data listing provided for TPO and EPO concentrations.

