2.2. Background

GSK2330811 is a humanised monoclonal antibody that binds and neutralises OSM and is being developed for the treatment of SSc and CD.

OSM is a member of the IL-6 family of cytokines, which is produced by a variety of immune cells including macrophages, activated T-cells and neutrophils in response to infection and tissue injury. OSM signalling on a variety of cell types, including fibroblasts, epithelial, endothelial, smooth muscle cells and hematopoietic cells, drives inflammation, fibrosis and vasculopathy [[Hermanns, 2015](#); [Ayaub, 2017](#)].

The safety profile of GSK2330811 has been evaluated in repeat-dose SC 13 and 26-week monkey toxicity studies. The key findings were of a reduction in red cell parameters in the peripheral blood and bone marrow with evidence of a regenerative reticulocyte response and of a transient reduction in platelet counts which showed partial to complete recovery by week 13. In the 13-week toxicity study, the no observed adverse effect level (NOAEL) was considered to be 300 mg/kg/week (the highest dose tested). In the 26-week toxicity study, because of the magnitude of the pharmacology related effects on red blood cell parameters noted the NOAEL was not identified. Of note, for non-pharmacology related findings the NOAEL is considered to be 300 mg/kg/week (highest dose tested). Detailed information can be found in the Investigator's Brochure (IB) for GSK2330811 [GlaxoSmithKline Document Number [2016N284919_02](#), 2019].

The safety, tolerability and PK of GSK2330811 has been evaluated in a Phase 1 single-dose escalation study in healthy volunteers (201246, NCT02386436, [[Reid, 2018](#)]). Thirty participants were exposed to GSK2330811 at doses ranging from 0.1 mg/kg to 6.0 mg/kg. GSK2330811 was well-tolerated, with no serious adverse events (SAEs) reported. The pharmacokinetic profile of GSK2330811 was consistent with that of an IgG1 monoclonal antibody against a soluble cytokine and high levels of target engagement were observed. A reversible reduction in platelet count was observed at dose levels of 1

mg/kg and above, and a low-grade reduction in haemoglobin and red cell count was observed at the highest dose level (6 mg/kg). Both these effects are consistent with the inhibition of the known pharmacology of OSM by GSK2330811. Detailed information can be found in the IB for GSK2330811 [GlaxoSmithKline Document Number [2016N284919_02](#), 2019].

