9.2. Sample Size Determination

There will be a minimum of 10 Japanese participants. The participants will be randomised in the ratio 7:3 to GSK2330811 (450 mg) or placebo.

From the number of adverse events of a specific type observed in 7 participants receiving GSK2330811, statistical inferences can be made about the 95% Credible Interval of the true event rate, as shown in Table 2, specifying a prior distribution (Beta [1,1]). The 95% CrI for 6 participants is also presented, as the sample size was defined with a view to

ensuring at least 6 participants receiving GSK2330811 are evaluable. Table 2 shows that if 0 particular safety events are observed out of 7 participants in the GSK2330811 group, the upper limit of the 95% Credible Interval indicates that a true event rate of 37% could not be ruled out.

Table 2 Upper 95% Credible Limit of the True Event Rate based on 7 participants on GSK2330811 completing the study

Observed events / participants in cohort	Lower 95% Credible Limit of true event rate	Upper 95% Credible Limit of true event rate
0/7	0.3%	37%
1/7	3.2%	53%
2/7	8.5%	65%
0/6	0.4%	41%
1/6	3.7%	58%
2/6	9.9%	71%

The values in Table 3 are the geometric means of PK parameters observed in the FTIH study 201246 following GSK2330811 SC administration:

Table 3 AUC and Cmax Geometric Means and Percent Coefficient of Variation (%CV_b) Observed in Caucasian PK Study 201246

Treatment group	Value (%CV _b)	
	AUC (0-inf) (h*ug/mL)	Cmax (ug/mL)
0.1 mg/kg	615 (26.2)	0.6 (32.3)
0.3 mg/kg	1605 (21.6)	1.5 (42.7)
1 mg/kg	5316 (42.5)	5.7 (43.5)
3 mg/kg	14656 (21.6)	19.0 (42.7)
6 mg/kg	27681 (23.3)	36.4(22.9)

The mean baseline weight in the 201246 study was 69.5kg and so the 6 mg/kg dose corresponds to an average dose of 417 mg; therefore, the PK parameters and CV_b %'s presented in Table 3 for the 6 mg/kg group are a good approximation for a dose of 450 mg.

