10.1.3. Population of Interest

The exploratory pharmacodynamics analyses will be based on the safety population, unless otherwise specified.

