12.9.9. Pharmacodynamic (and / or Biomarker) Tables

Pharmacodynamic (and or Biomarker): Tables					
No.	Population	IDSL / Example Shell	Title	Programming Notes	Deliverable [Priority]
Serum level of OSM					
6.1.	Safety	PD1	Summary of Serum Level of Free OSM by Treatment Group	Calculate confidence intervals and add number imputed Add footnote: [1] No. of subjects with BLQs assigned half of the lower limit of quantification (LLQ = 2.5pg/ml)	SAC
6.2.	Safety	PD1	Summary of Serum Level of Total OSM by Treatment Group	Calculate confidence intervals and add number imputed Add footnote: [1] No. of subjects with BLQs assigned half of the lower limit of quantification (LLQ = 2.5pg/ml)	SAC
6.3.	Safety	PD1	Summary of Ratio of Serum Level of Total OSM to Baseline by Treatment Group	Calculate confidence intervals and add number imputed Add footnote: [1] No. of subjects with BLQs assigned half of the lower limit of quantification (LLQ = 2.5pg/ml)	SAC
6.4.	Safety	PD2	Summary of Log Transformed Serum Level of Total OSM by Treatment Group	Calculate confidence intervals and add number imputed Add footnote: [1] No. of subjects with BLQs assigned half of the lower limit of quantification (LLQ = 2.5pg/ml)	SAC

CONFIDENTIAL

208564

Pharmacodynamic (and or Biomarker): Tables					
No.	Population	IDSL / Example Shell	Title	Programming Notes	Deliverable [Priority]
6.5.	Safety	PKPT1	Summary of Derived Serum Pharmacokinetic Parameters of Total OSM by Treatment Group		SAC
6.6.	Safety	PKPT3	Summary of Log-Transformed Derived Serum Pharmacokinetic Parameters of Total OSM by Treatment Group		SAC

CONFIDENTIAL

208564

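### The SAP lists dose-based and extrapolated NCA parameters for total OSM, which is endogenous and never dosed, with placebo included and no baseline correction

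*SAP*

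**What the plan says.** SAP 10.1.2 opens firmly: "Total OSM parameters will be calculated by standard non-compartmental analysis according to current working practices". The sentence that names the parameters is permissive. It lists Cmax, Tmax, AUC(0-t), AUC(0-inf), %AUCex and t1/2, and continues "CL/V, Vss/V, tlast might be calculated with non-compartmental analysis", using the serum data and only so far as those data allow.

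The displays are scheduled in SAP 12.9.9:

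- Table 6.5: "Summary of Derived Serum Pharmacokinetic Parameters of Total OSM by Treatment Group".
- Table 6.6: "Summary of Log-Transformed Derived Serum Pharmacokinetic Parameters of Total OSM by Treatment Group".

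Both use the Safety population and the display shells of the drug PK parameter tables (4.2 and 4.3). Listing 31 in SAP 12.9.13 gives the individual values, also on the Safety population. SAP 10.1.3 sets the general rule: "The exploratory pharmacodynamics analyses will be based on the safety population, unless otherwise specified". Placebo participants are therefore in all three displays.

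On the analyte, Protocol 2.2 says "OSM is a member of the IL-6 family of cytokines, which is produced by a variety of immune cells". The only active substance given is the antibody: "The participants will be randomised in the ratio 7:3 to GSK2330811 (450 mg) or placebo" (Protocol 9.2).

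Three things are not stated. CL/V and Vss/V are defined nowhere; SAP 9.1.1.2 and 12.8.1 define only CL/F and Vss/F. SAP 10.1.2 applies the ratio to baseline to concentrations and says nothing of baseline for the NCA. The 20% limit on extrapolated area stands in SAP 9.1.1.2 for the drug and is not repeated for OSM.

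**The concern.** The list appears to carry the drug's parameter set over to a molecule that behaves differently. Clearance and volume relate a known dose to the resulting exposure, and OSM has no dose. Terminal half-life and AUC to infinity assume that the concentration declines to zero, whereas an endogenous cytokine declines to its own baseline. A placebo participant has no treatment-induced rise, so any terminal slope is noise.

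Protocol 4.4 says that the exploratory endpoints were chosen to confirm target engagement and examine PK/PD relationships. A reader could take an OSM half-life in Table 6.5 as the turnover of the drug-target complex when part of it reflects the baseline, or could compare it with a placebo half-life that means nothing.

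**Working it through.** The documents give no figure for the OSM parameters, so there is nothing to reproduce. The first step needs no data. The other two use assumed profiles.

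**1. Clearance and volume.** By the usual definitions, CL/F = dose / AUC(0-inf), and Vss/F is CL/F multiplied by a mean residence time. Both need a dose of the measured substance. SAP 12.5.2 records 0 mg for placebo and 150 mg of antibody per injection otherwise. Putting 450 mg of antibody over an OSM area mixes two molecules; putting 0 over it gives zero. Neither describes OSM.

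**2. Half-life and AUC(0-inf) in the active arm.** The SAP 9.1.1.2 formulas are t1/2 = ln 2 / λz and AUC(0-inf) = AUC(0-t) + C(t)/λz.

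- From the documents: OSM sampling at pre-dose, 8 h and Days 2, 3, 5, 7, 10, 14, 21, 28, 42, 56, 84 and 126; drug half-life 19 to 25 days (Protocol 4.4).
- Assumed: baseline 1; rise half-life 4 days; decline half-life 19 or 25 days; peak R times baseline; no noise.
- Model: C(t) = 1 + (R − 1)·f(t), where f(t) is exp(−ke·t) − exp(−ka·t) scaled to a maximum of 1, ke = ln 2/19 or ln 2/25, and ka = ln 2/4.
- λz is the best adjusted R² fit on at least 3 points after Cmax. AUC uses the linear-up, log-down rule.

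| True t1/2 | R | Uncorrected t1/2 (days) | Extrapolated area |
|---|---|---|---|
| 19 d | 3 | 75.5 | 35% |
| 19 d | 10 | 35.6 | 11% |
| 19 d | 30 | 25.5 | 4% |
| 19 d | 100 | 21.4 | 2% |
| 25 d | 3 | 76.6 | 35% |
| 25 d | 10 | 39.0 | 13% |
| 25 d | 30 | 30.1 | 7% |
| 25 d | 100 | 26.8 | 5% |

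Check of the first row. At Day 126 (t = 125 days), f = 0.0201, so C = 1 + 2 × 0.0201 = 1.040, and 1/1.040 = 96% of the last value is baseline. The extrapolated piece is 1.040 × 75.5 / 0.693 = 113. With AUC(0-t) = 208, its share is 113/321 = 35%. At R = 100 the last value is 1 + 99 × 0.0201 = 2.99, of which 1/2.99 = 33% is baseline.

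After subtracting the baseline, the same code returns 19.1 and 25.1 days at every R, with 1.3% and 3.8% extrapolated. In the first row AUC(0-inf) falls from 321 to 83.

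A 20% extrapolation limit alone would not catch the bias. At R = 10 and a true 19 days, the uncorrected half-life is nearly doubled (35.6/19 = 1.9) while only 11% of the area is extrapolated.

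**3. Placebo.** Assumed: a flat, quantifiable baseline with log-SD 0.1, 0.2 or 0.3; 5,000 profiles each; same λz rule.

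| Log-SD | Profiles yielding a half-life | Median t1/2 (5th–95th percentile), days | Median extrapolated area |
|---|---|---|---|
| 0.1 | 56.5% | 728 (215–11,694) | 89% |
| 0.2 | 57.4% | 342 (106–5,111) | 79% |
| 0.3 | 56.7% | 231 (72–3,681) | 71% |

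The simulated decline is nil, so every half-life is chance. At least 99.9% of profiles that yielded one had more than 20% extrapolated. The figures depend on the assumptions: over the terminal-point rules and noise levels tried, the share with no estimate ran from 26% to 63% and the median half-life from about 140 to 1,300 days.

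**The case against.** The strongest defence is that the plan does not commit to these parameters. The naming sentence is permissive and conditional on the data, the entries for Tables 6.5 and 6.6 list no parameters, and displays holding only Cmax, Tmax and AUC(0-t) would satisfy them. A reader might infer from the scheduled tables that clearance, volume and half-life will be reported; the documents do not say so. What remains is that the SAP gives no criterion for when OSM data permit, and software can return a half-life whenever noise slopes downward.

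A reader might also infer that none of these parameters has a valid meaning in either arm. That goes too far. On active treatment, an apparent half-life or AUC(0-inf) can describe the drug-target complex, either when the rise over baseline is large or after the baseline is subtracted. Only clearance and volume fail in both arms.

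The artefacts in t1/2 and AUC(0-inf) presuppose a quantifiable baseline, and no OSM baseline is given. SAP 12.4.4 sets non-quantifiable values before the first measurable one to zero and drops those after the last one from parameter derivation, so a wholly non-quantifiable placebo profile would yield no half-life. SAP 12.6.2.2 instead imputes half the LLQ for summaries, plots and analysis, so the treatment of such values is not settled. The condition has to stay in the conclusion.

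Finally, a reader might infer that the target engagement result is compromised. The exploratory endpoints are OSM levels, covered by Tables 6.1 to 6.4 and Figures 6.1 to 6.3 and 7.1. No passage makes a decision depend on an OSM half-life.

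**Conclusion.** The point holds in limited form. CL/V and Vss/V are undefined and, read as clearance and volume, have no valid computation in either arm. That reading is an inference, since they may be slips for CL/F and Vss/F, but those need a dose too.

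Where baseline OSM is quantifiable, half-life and AUC(0-inf) are artefacts in placebo. On active treatment they are biased upward by an amount set by the rise over baseline: negligible to modest at 100-fold, about three- to fourfold for half-life at 3-fold (76.6/25 = 3.1; 75.5/19 = 4.0). These sizes rest on assumed fold rises, noise and curve shape.

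The consequence is confined to an optional part of an exploratory analysis. No primary or secondary result changes, so this is a worthwhile tidy-up and not a threat to the study.

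**What to change.** In SAP 10.1.2, and in the notes to Tables 6.5 and 6.6 and Listing 31:

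- Delete CL/V and Vss/V for total OSM.
- Keep Cmax, Tmax and AUC(0-t), or an AUC over a fixed interval, for both arms, observed and baseline-corrected. A fixed interval needs a rule for early withdrawals and for the ±7-day window at Day 126.
- Report t1/2, AUC(0-inf) and %AUCex for the active arm only, after baseline correction, and withhold AUC(0-inf) when extrapolation exceeds the 20% limit of SAP 9.1.1.2.

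The cost is SAP wording and a little programming, with no new data. Some participants will have no reportable half-life or AUC(0-inf), because baseline-corrected values late in follow-up can be small and noisy.

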9.4.4. Exploratory Endpoints

- Summary statistics will be produced where appropriate by time point and treatment group.
- Graphical displays will be produced over time for serum free and total OSM, TPO and EPO levels.
- Exploratory PK/PD analyses, if data permit, may be completed on selected free and total OSM measurements to examine the relationship between plasma concentrations of GSK2330811, and target OSM concentration (free and total).
- Exploratory PK/PD analyses, if data permit, may be conducted on the platelet endpoint to examine the relationship between plasma concentrations of GSK2330811, and platelet count.

Full details of planned exploratory analysis will be specified in the RAP.

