3. ANALYSIS POPULATIONS

Population	Definition / Criteria	Analyses Evaluated
Screened	
 • All participants who signed the ICF and were screened for eligibility 	
 • Study Population • Screen Failures
Enrolled	
 • All participants who signed the ICF and were randomized into the study. 	
 • Study Population
Safety	
 • All randomized participants who received a full dose of study treatment. • Participants will be analysed according to the treatment they received. • Note: In the very unlikely case a participant is not randomized but receives at least one dose of study treatment, these participants will be listed separately. 	
 • Study Population • Safety • PK/PD selected tables and figures
Pharmacokinetic (PK)	
 • All participants in the Safety population who received at least one active dose of study treatment and had at least 1 non-missing PK assessment (Non-quantifiable values will be considered as non-missing values). • Participants will be analysed according to the study treatment they received. 	
 • PK • PK/PD selected figures

Refer to [Appendix 9](#): List of Data Displays which details the population used for each display.

CONFIDENTIAL

208564

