10.1.5. Statistical Analyses / Methods

Details of the planned displays are provided in [Appendix 9](#): List of Data Displays and will be based on GSK Data Standards and statistical principles.

Unless otherwise specified, endpoints / variables defined in Section [10.1.1](#) will be summarised using descriptive statistics, graphically presented (where appropriate) and listed.

CONFIDENTIAL

208564

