12.9.13. Non-ICH Listings

Non-ICH: Listings					
No.	Population	IDSL / Example Shell	Title	Programming Notes	Deliverable [Priority]
PK concentration and derived PK parameters					
28.	PK	PKCL1	Listing of GSK2330811 Plasma Concentration-Time Data	Add data dependent footnote: 'Note: NA=Not Available [data dependent], NQ=Non-Quantifiable, LLQ value=100ng/mL'	SAC
29.	PK	PKCL1	Listing of Derived GSK2330811 Pharmacokinetic Parameters		SAC
Serum levels of OSM					
30.	PK	PKCL1	Listing of Serum Level of OSM	Include both Free and Total OSM Add footnote: 'Note: BLQ = Below the limit of quantification which is 2.5pg/ml for both free and total OSM'	SAC
31.	Safety	PKCL1	Listing of Derived Total OSM Pharmacokinetic Parameters		SAC
Serum levels of TPO and EPO					
32.	PK	PKCL1	Listing of Level of Thrombopoietin in Serum		SAC
33.	PK	PKCL1	Listing of level of Erythropoietin in Plasma		SAC
Other					
34.	Enrolled	PAN12	Listing of COVID-19 Assessments and Symptom Assessments for Subjects with COVID-19 Adverse Events		SAC
35.	Enrolled	PAN7	Listing of All Subjects with Visits and Assessments Impacted by COVID-19 Pandemic		SAC

CONFIDENTIAL

208564

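### As written, no planned display shows placebo TPO or EPO, and the plots over time that the protocol promises for free OSM, TPO and EPO are dropped without being declared

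*SAP*

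**What the plan says.** Protocol section 9.4.4 makes an unqualified commitment on graphics: "Graphical displays will be produced over time for serum free and total OSM, TPO and EPO levels". The neighbouring items in that section are hedged: summary statistics are to be given where appropriate, and the PK/PD analyses may be done. This one is not. The section leaves full details to the reporting and analysis plan.

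SAP section 10.1.2 plans plots for total OSM only and then states: "Only data listing provided for TPO and EPO concentrations". In Appendix 9, section 12.9.13, the TPO display is Listing 32, "Listing of Level of Thrombopoietin in Serum", and EPO is Listing 33. Both have PK in the population column, as does Listing 30 (free and total OSM). Listing 31, "Listing of Derived Total OSM Pharmacokinetic Parameters", uses the same shell but is on the Safety population.

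SAP section 3 defines the PK population as "All participants in the Safety population who received at least one active dose of study treatment", with at least one non-missing PK assessment. It refers the reader to Appendix 9 as the "List of Data Displays which details the population used for each display".

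Two general clauses point the other way. Section 10.1.3 says "The exploratory pharmacodynamics analyses will be based on the safety population, unless otherwise specified". Section 10.1.5 says the PD endpoints, unless otherwise specified, "will be summarised using descriptive statistics, graphically presented (where appropriate) and listed". Section 2.1, which records changes from the protocol's analysis plan, mentions only the unplanned interim analysis.

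**The concern.** TPO and EPO are measured to help explain the platelet and haemoglobin reductions seen with this antibody (protocol section 8.6.2). Thrombocytopenia and anaemia are the first two risks in the protocol's risk table. The placebo arm is justified in protocol section 4.4 partly as a source of PD control data. A programmer who follows Appendix 9 literally will produce TPO and EPO listings with no placebo participants in them, and nothing else in the plan shows these analytes.

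Each active participant's pre-dose value would still be there to compare with. What would be missing is any concurrent reference for drift over time or for the effect of repeated blood sampling. The comparison would only ever be descriptive, with about three placebo participants and no inference planned, but describing the data is all the plan sets out to do.

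Separately, a reader of the protocol would expect plots for four analytes and would find them for one, with no statement that the plan had changed.

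**Working it through.** No sample size, power or error rate is involved. The check compares the protocol's commitments with every relevant entry in SAP Appendix 9 and then counts the results affected.

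**1. Displays by analyte (SAP sections 12.9.9 to 12.9.13)**

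| Analyte | Tables | Figures over time | Listing | Placebo shown? |
|---|---|---|---|---|
| Total OSM | 6.2 to 6.6 (Safety) | 6.1 to 6.3 (Safety) | 30 (PK), 31 (Safety) | Yes |
| Free OSM | 6.1 (Safety) | none | 30 (PK) | Summary only, not by participant |
| TPO | none | none | 32 (PK) | No |
| EPO | none | none | 33 (PK) | No |

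Figure 7.1 plots total OSM against drug concentration on the PK population, so it is not a plot over time and does not involve the other three analytes.

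**2. Could another display carry TPO or EPO?** No. Neither is among the safety laboratory tests in protocol Appendix 2. Listing 19 is haematology, Listings 20 and 21 are haematology and chemistry, and Listing 22 is laboratory data with character results.

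**3. Do the general clauses restore them?** No. Sections 10.1.3 and 10.1.5 both give way where something else is specified. Section 10.1.2 specifies listing only for TPO and EPO, Appendix 9 specifies PK, and section 3 makes Appendix 9 the place where each display's population is set. For free OSM, section 10.1.5 names no figure and Appendix 9 contains none.

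**4. Plots promised against plots planned.** Promised: 4 analytes (protocol section 9.4.4). Planned: 1 (total OSM). Missing: 4 − 1 = 3. Declared in SAP section 2.1: 0.

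**5. Results affected.** Inputs:
- Five analysis timepoints per analyte (SAP section 12.2.1): EPO at Days 1, 7, 14, 21 and 56; TPO at Days 1, 5, 10, 21 and a last one labelled Day 86.
- About 2 mL of blood per biomarker per timepoint (protocol section 8.6.2).
- 7:3 allocation; about 10 dosed, at most 14 (protocol section 4.2); at most 4 replacements (SAP section 12.6.1), each to the same arm.

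Per participant: 5 × 2 = 10 results, from 10 × 2 mL = 20 mL of blood.

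The number actually dosed is not in the documents, so the counts below are scenarios that assume complete sampling:

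| Scenario | All results | Placebo results in no display |
|---|---|---|
| 10 dosed, 7:3 | 10 × 10 = 100 | 3 × 10 = 30 (30%) |
| 14 dosed, all four replacements active | 14 × 10 = 140 | 3 × 10 = 30 (21%) |
| 14 dosed, three of four replacements placebo | 14 × 10 = 140 | 6 × 10 = 60 (43%) |

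Replaced participants may have incomplete sampling, so the result counts are ceilings.

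**The case against.** The strongest reply is that the PK label is a clerical slip. Safety is the stated default for exploratory PD. Section 3 assigns the PK population to PK and selected PK/PD figures, not to biomarker listings. Listing 31 uses the same shell on Safety. SAP section 12.2 defines EPO and TPO windows for summaries and figures, and says PD assessments will be summarised and listed. On that reading nobody decided to leave out placebo. This may well be so, but it is a reason to correct the label: the display list controls what is programmed, and it says PK.

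Second, the narrowing is stated openly in section 10.1.2, and the protocol leaves full details to the reporting plan. Openness stands as a mitigating point. But leaving detail to a later document does not cover removing displays that the protocol says will be produced, and section 2.1 exists to record such changes.

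Third, active participants have their own baselines, the endpoints are exploratory, and the counts above are numbers of samples, not effects on a conclusion. All of this stands, and it limits the weight of the point without removing it. It is also true that the protocol's graphics sentence says only that plots are over time. Splitting them by arm is a recommendation here, not a protocol commitment.

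**Conclusion.** The concern holds. Read literally, the SAP displays no placebo TPO or EPO result, whatever number is dosed. Three of the four analytes with promised plots over time have none, and section 2.1 does not say so. In addition, placebo free OSM is summarised in Table 6.1 but not listed by participant.

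The conclusion rests on the Appendix 9 population column being followed as written. The 21% to 43% range rests on the sampling and replacement assumptions shown above.

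The reach is limited. No primary or secondary output is affected: platelets and haemoglobin are shown by arm on the Safety population, and placebo free and total OSM are summarised in Tables 6.1 to 6.4. It should be corrected because the correction is cheap and recovers the PD control data that the placebo arm was partly included to provide.

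**What to change.** 1. In SAP section 12.9.13, change the population for Listings 32 and 33 from PK to Safety. Do the same for Listing 30, so that placebo free OSM is listed by participant.
2. In SAP section 10.1.2, replace the listing-only sentence with plots over time by treatment group for TPO, EPO and free OSM, and add the three figures to section 12.9.10. If any plot is deliberately omitted, record the omission and its reason in section 2.1. That alternative settles the documentation but does not by itself show the placebo data, so item 1 is needed either way.
3. A separate, minor tidy-up: section 12.4.4 sets most non-quantifiable total OSM values to zero in mean and median profiles, while section 12.6.2.2 and the table and figure footnotes use LLQ/2. State that the LLQ/2 rule governs total OSM summaries and plots, and align the number-imputed wording in 12.4.4 with the footnotes to Tables 6.2 to 6.4.

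The cost is three population labels, three small figures and a few lines of text. The samples and assays are already planned.
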